6.5 Demographic and Other Baseline Characteristics

Demographic and baseline characteristics summaries will be done for the ITT, Safety, and PP populations.

Sex, race, and ethnicity will be summarized by counts and percentages. Age, height (cm), and weight (kg) will be summarized with descriptive statistics.

IGA PN-A, and IGA PN-S will be summarized by counts and percentages. WI-NRS (average result measured over the week prior to treatment) and DLQI will be summarized with descriptive statistics.

Medical histories will be coded using MedDRA, tabulated by System Organ Class and Preferred Term for the Safety population, and presented in a by-subject listing.

PN history and prior PN therapies will be presented in by-subject listings.

6.6 Prior and Concomitant Medications

Prior and concomitant medications will be coded by the WHO-DDE to Anatomical Therapeutic Classification (ATC) and preferred drug name. Concomitant medications will be summarized by ATC level 2 term and preferred drug name.

A by-subject listing of all prior and concomitant medications will be presented. The associated by-subject listing will have a prior/concomitant determination that is based on the date of first dose.

6.7 Analysis of Efficacy

The efficacy endpoints will be summarized within the ITT and PP populations using descriptive statistics by time point and treatment. Available results including averaged imputed values, as well as change from baseline, will be summarized for each applicable time point. The WI-NRS and change from baseline will also be presented for each study day in a by-subject listing.

For the 4- and 3-point responder rate endpoints, subjects will be considered responders if they have at least a 4- / 3-point reduction between baseline and the corresponding week. Subjects that discontinued study drug due to lack of efficacy or used an excluded medication to treat worsening of pruritus or PN will be considered non-responders.

6.7.1 Primary Efficacy Analysis

The difference in the primary efficacy outcome measure (WI-NRS 4-point responder rate at Week 10) will be tested using a CMH test controlling for the ‘as randomized’ stratification factors. Conceptually the hypotheses being tested are:

$$H_0: P_{Placebo} \geq P_{Serlopitant}$$

$$H_a: P_{Placebo} < P_{Serlopitant}$$

where $P_{Placebo}$ is the percent of placebo responders and $P_{Serlopitant}$ is the similar percent for serlopitant.

6.7.2 Key Secondary Efficacy Analysis

The WI-NRS 4-point responder rates at Week 4 and Week 2 will be analyzed using methods consistent with testing the primary endpoint.

The preceding analyses are to be conducted for the ITT and PP populations.

6.7.3 Additional Secondary Efficacy Analysis

Additional secondary efficacy endpoints which may be drawn from the primary and key secondary imputations (including all WI-NRS endpoints) will be analyzed using the imputed data. Additional secondary efficacy endpoints otherwise will be analyzed using available data. P-values will be included for descriptive purposes only.

Additional secondary efficacy endpoints which are dichotomous (responder) will include analyses analogous to the primary and key secondary efficacy analyses.

Additional secondary efficacy endpoints based on change from baseline will be analyzed using an analysis of covariance (ANCOVA) model with treatment group and stratification factor as fixed effects and the baseline value as a covariate. Both least squares means and observed means will be presented.

To confirm the assumptions for the ANCOVA model (i.e., that the errors are normally distributed with equal variances), residuals will be examined using the Shapiro-Wilk test. If there is overwhelmingly strong evidence that the assumptions are not satisfied, the data will be rank-transformed prior to submitting to the ANCOVA. Results of the rank-transformed analysis then will be considered the primary analysis; however, results of the non-rank transformed analysis will also be presented.

6.8 Sensitivity Analysis

6.8.1 Last Observation Carried Forward

In the first set of sensitivity analyses, missing values will be imputed using LOCF. Data will be imputed using LOCF unless the subject withdrew from the study due to lack of efficacy, or the subject used an excluded therapy to treat worsening of pruritus or PN, in which case their responder status will be defined as non-responder. Each primary and key secondary endpoint will be analyzed as it was using the multiply imputed data.

6.8.2 Repeated Measures Analysis

The second set of sensitivity analyses will be performed on observed data.

The dichotomized primary and key secondary WI-NRS endpoints will each be analyzed with a repeated measures logistic regression model (generalized estimating equations), with the dichotomized endpoint as the dependent variable and treatment, stratification factor and visit (Weeks 1-10) as independent factors.

6.8.3 Tipping Point Analysis

A sensitivity analysis for the handling of missing data for the primary efficacy endpoint will be carried out using a tipping point analysis. Specifically, a range of response rates for both groups will be explored to determine the tipping point(s) at which the combinations result in no longer reaching statistical significance.

6.9 Safety Evaluation

6.9.1 Extent of Exposure

The extent of exposure to study drug in each treatment group will be summarized by days with exposure and total number of tablets used.

A subject will be considered compliant with the dosing regimen if the subject takes 80% to 120% of the expected number of doses while enrolled in the study. Total number of days of exposure will be computed as follows:

$$\text{Total Exposure} = \text{Date of Last Dose} - \text{Date of First Dose} + 1$$

$$\begin{aligned} \text{Total Doses} &= (\text{Date of Last Dose} - \text{Date of First Dose} + 1 + 2) \\ &\quad - \text{Missed Doses} + \text{Extra Doses} \end{aligned}$$

Treatment compliance will be based on the expected number of doses given the treatment period duration. The number of expected doses will be computed from the Baseline/Day 1 visit date and the Week 10 visit date. If a subject does not have a Week 10 visit, the number of expected doses will be calculated based on end of treatment period date given available information (e.g., date of last dose, last completed visit date).

$$\text{Expected Doses} = \text{End of Treatment Period Date} - \text{Day 1 Date} + 2$$

If the subject is documented as dosing on the End of Treatment Period Date, a dose will be added to the Expected Doses. To allow for the +7 day window around Week 10 that is used for defining PP population, if the number of expected doses exceeds 80, the number of expected doses will be considered 80 doses.

Percent compliance will be calculated from total number of doses and total number of expected doses as follows:

$$\text{Percent Compliance} = 100 * (\text{Total Doses} / \text{Expected Doses}).$$

Percent compliance will not be calculated for subjects who are lost to follow-up during the treatment period.

6.9.3 Clinical Laboratory Evaluation

Clinical safety laboratory values will be measured by a central laboratory. Summary statistics for actual values and for changes from baseline will be tabulated for laboratory results by scheduled visit.

Subjects with clinical laboratory values outside of the normal reference range at any post-baseline assessment will be summarized. Shifts from baseline laboratory values will be tabulated, with the exception of most reproductive endocrinology laboratory values.

Serum follicle-stimulating hormone, luteinizing hormone, estradiol, progesterone and anti-mullerian hormone will be summarized separately for women using hormonal contraception/therapies and those not using hormonal contraception/therapies.

By-subject listings of all laboratory data, as well as abnormal laboratory results, will be presented.

6.9.4 Other Observations Related to Safety

6.9.4.1 ECG Measurements

Summary statistics for actual values and for changes from baseline will be tabulated for ECG parameter results by scheduled visit. The overall ECG assessment (abnormal or normal) will be summarized along with a summary of how many subjects developed a post treatment abnormal result. The study relevance of the finding (i.e. clinical significance as determined by the investigator) will be provided in a by-subject listing.

6.9.4.2 Vital Signs

The observed data and change from baseline for each measurement day will be summarized with descriptive statistics, as well as provided in a by-subject listing.

6.9.4.3 Physical Exams

Clinically significant physical exam findings will be recorded by the sites within medical history or adverse events and otherwise not summarized.

6.9.4.4 Menstrual Diaries

Menstrual diary dates will be used to summarize number and duration of menses.

6.9.4.5 Hospital Anxiety and Depression Scale (HADS)

The observed data and change from baseline for the HADS will be summarized with descriptive statistics by scheduled visit. Both the Depression and Anxiety subscales will be reported.

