- Female subjects should be queried for presence of new breast masses or abnormal discharge, and abnormal vaginal bleeding or discharge
- Review menstrual diary and record dates of menstrual flow (if applicable)
- Obtain ECG
- Obtain vital signs
- Perform targeted physical examination, including weight
- Perform IGA PN-A
- Perform IGA PN-S
- Draw blood for clinical laboratory tests
 - Hematology
 - Chemistry
- Collect PK blood sample
- Assess and record any AEs and SAEs
- Review eDiary for compliance, re-train subject as needed
- Review study drug compliance with re-training as required
- Collect returned study drug

- Utilize IWRS to assign new bottle of study drug
- Confirm next scheduled visit date

6.5.7 *Week 4 Visit*

The Week 4 visit occurs 28 days (\pm 3 days) after the Baseline visit. At the Week 4 visit, the following procedures and assessments are to be performed:

- Ask the subject to complete the DLQI, HADS, and ESS questionnaires
- Assess and record any changes in the subject's concomitant medications
- Female subjects should be queried for presence of new breast masses or abnormal discharge, and abnormal vaginal bleeding or discharge
- Review menstrual diary and record dates of menstrual flow (if applicable)
- Obtain ECG
- Obtain vital signs
- Perform a urine pregnancy test for females of childbearing potential (with positive or equivocal results confirmed by a serum pregnancy test)
- Perform targeted physical examination, including weight
- Perform IGA PN-A
- Perform IGA PN-S
- Collect PK blood sample
- Assess and record any AEs and SAEs
- Collect returned study drug
- Utilize IWRS to assign new bottle of study drug
- Review eDiary for compliance, re-train subject as needed
- Review study drug compliance with re-training as required
- Confirm next scheduled visit date

6.5.8 *Week 6 Visit*

The Week 6 visit occurs 42 days (\pm 3 days) after the Baseline visit. At the Week 6 visit, the following procedures and assessments are to be performed:

- Assess and record any changes in the subject's concomitant medications
- Female subjects should be queried for presence of new breast masses or abnormal discharge, and abnormal vaginal bleeding or discharge
- Review menstrual diary and record dates of menstrual flow (if applicable)
- Obtain vital signs
- Perform a urine pregnancy test for females of childbearing potential (with positive or equivocal results confirmed by a serum pregnancy test)

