5.2 Safety Endpoints

Safety endpoints include the following:

- Incidence of treatment-emergent adverse events (TEAEs) and serious adverse events (SAEs)
- Changes from baseline in clinical laboratory parameters following study drug exposure
- Changes from baseline in vital sign and electrocardiogram (ECG) parameters following study drug exposure
- Change from baseline in the Hospital Anxiety and Depression Scale (HADS)
- Change from baseline in the Epworth Sleepiness Scale (ESS)

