6.1.3 Visit Windowing

Data will be summarized based on nominal visit indications. Data collected during post-treatment follow-up will be summarized as

Protocol Version(s)	Nominal Visit	Analysis Visit
V2.0; V2.1	3-Week Follow-up	3-Week Follow-up
V2.0; V2.1	5-Week Follow-up	5-Week Follow-up

In addition, a “Latest Follow-up” visit will be summarized, which will include the latest available follow-up information for each subject from the 3-, 5- Week Follow-up visits.

Information collected at early treatment discontinuation visits will be mapped to the most appropriate visit based on the midpoints between scheduled visits.

For example, if a subject terminates use of study drug on or after Day 22 but before Day 36, data collected at the early end of treatment visit will be mapped to the Week 4 evaluation for summaries. If the subject has Week 4 values present, the data collected at the early end of

treatment visit will not replace the data collected at Week 4. For the sensitivity efficacy analyses, last observation carried forward (LOCF) will be applied subsequent to mapping the information to the appropriate visit.

Additionally, WI-NRS will be summarized at Weeks 1, 2, 3, 4, 5, 6, 7, 8, 9, 10 and 3- and 5-Week Follow-up by averaging the daily results for the 7 days prior to each week. The weekly average values will be calculated if a subject has at least four responses during the 7 day range, as defined below:

Week/Visit	Study Day Range
Week 1	2-7 (as Day 1 may be pre or post first dose)
Week 2	8-14
Week 3	15-21
Week 4	22-28
Week 5	29-35
Week 6	36-42
Week 7	43-49
Week 8	50-56
Week 9	57-63
Week 10	64-70
3-Week Follow-up	Post-treatment days 15-21
5-Week Follow-up	Post-treatment days 29-35

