6.9.4.6 Epworth Sleepiness Scale (ESS)

The observed data and change from baseline for the ESS will be summarized with descriptive statistics by scheduled visit.

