Table to include parameters in following order: “Temperature (degrees Celsius)”, “Respiration Rate (breaths/min)”, “Heart Rate (beats/min)”, “Systolic Blood Pressure (mmHg)”, “Diastolic Blood Pressure (mmHg)”.

Table to include post-baseline visits of “Week 2”, “Week 4”, “Week 6”, “Week 10”, “3-Week Follow-up”, “5-Week Follow-up”, “Latest Follow-up”.

Table 14.3.1.7.1: Summary of Hospital Anxiety and Depression Scale (HADS)
(Safety Population)
(Page 1 of xx)

<Subscale>	Placebo (N=xxx)	Serlopitant 5 mg (N=xxx)
Baseline		
n	xx	xx
Mean	xx.x	xx.x
SD	xx.xx	xx.xx
Median	xx.x	xx.x
Min. to Max.	xx to xx	xx to xx
Week 4		
n	xx	xx
Mean	xx.x	xx.x
SD	xx.xx	xx.xx
Median	xx.x	xx.x
Min. to Max.	xx to xx	xx to xx
Absolute Change from Baseline		
n	xx	xx
Mean	xx.x	xx.x
SD	xx.xx	xx.xx
Median	xx.x	xx.x
Min. to Max.	xx to xx	xx to xx

Note: Baseline is the latest recorded value prior to first dose of study drug. Change calculated as post-baseline – baseline. “Latest Follow-up” visit includes the latest available follow-up information for each subject from the 3-Week or 5-Week Follow-up visits.

SOURCE: USERNAME\SPONSOR\PROJECT\JOBNAME (DATE,TIME)

Table to include subscales in following order: “Anxiety Subscale”, “Depression Subscale”.

Table to include post-baseline visits of “Week 4”, “Week 10”, “3-Week Follow-up”, “5-Week Follow-up”, “Latest Follow-up”.

Table 14.3.1.8.1: Summary of Epworth Sleepiness Scale (ESS)
(Safety Population)
(Page 1 of xx)

	Placebo (N=xxx)	Serlopitant 5 mg (N=xxx)
ESS		
Baseline		
n	xx	xx
Mean	xx.x	xx.x
SD	xx.xx	xx.xx
Median	xx.x	xx.x
Min. to Max.	xx to xx	xx to xx
Week 4		
n	xx	xx
Mean	xx.x	xx.x
SD	xx.xx	xx.xx
Median	xx.x	xx.x
Min. to Max.	xx to xx	xx to xx
Absolute Change from Baseline		
n	xx	xx
Mean	xx.x	xx.x
SD	xx.xx	xx.xx
Median	xx.x	xx.x
Min. to Max.	xx to xx	xx to xx

Note: Baseline is the latest recorded value prior to first dose of study drug. Change calculated as post-baseline – baseline. “Latest Follow-up” visit includes the latest available follow-up information for each subject from the 3-Week or 5-Week Follow-up visits.

SOURCE: USERNAME\SPONSOR\PROJECT\JOBNAME (DATE,TIME)

Table to include post-baseline visits of “Week 4”, “Week 10”, “3-Week Follow-up”, “5-Week Follow-up”, “Latest Follow-up”.

CONFIDENTIAL

Table 14.3.1.9: Summary of Pharmacokinetic Concentrations
(Safety Population)

<Analyte> (<units>)	Placebo (N=xxx)	Serlopitant 5 mg (N=xxx)
Week 2		
n	xx	xx
Mean	xx.x	xx.x
SD	xx.xx	xx.xx
Median	xx.x	xx.x

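### HADS and ESS scores taken at early treatment discontinuation can map to visits that have no row in the safety tables

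*SAP*

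**What the plan says.** SAP 5.2 lists change from baseline in HADS and in ESS as safety endpoints. For analysis, SAP 6.9.4.5 says "The observed data and change from baseline for the HADS will be summarized with descriptive statistics by scheduled visit", and 6.9.4.6 says "The observed data and change from baseline for the ESS will be summarized with descriptive statistics by scheduled visit".

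Shells 14.3.1.7.1 (HADS) and 14.3.1.8.1 (ESS) show, by arm, n, mean, SD, median and min-max of the score and of its absolute change. Both carry the same programming note on visits: "Table to include post-baseline visits of “Week 4”, “Week 10”, “3-Week Follow-up”, “5-Week Follow-up”, “Latest Follow-up". Only the first two of these are on treatment.

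In Protocol version 4.0 the instruction "Ask the subject to complete the DLQI, HADS, and ESS questionnaires" stands at Baseline (6.5.4), Week 4 (6.5.7) and Week 10 (6.5.9), but not at Weeks 2 or 6. Appendix A Table 2 also marks HADS and ESS at follow-up and at Early Treatment Discontinuation.

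For that last visit SAP 6.1.3 says: "Information collected at early treatment discontinuation visits will be mapped to the most appropriate visit based on the midpoints between scheduled visits". Its example assigns the data to Week 4 "if a subject terminates use of study drug on or after Day 22 but before Day 36". It adds that, where a Week 4 value is present, data from the early end of "treatment visit will not replace the data collected at Week 4".

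**The concern.** The protocol takes the trouble to collect both scales when a subject stops drug, yet the general mapping rule can send that score to Week 2 or Week 6, where these two tables have no row. The by-arm on-treatment summary then describes mainly the subjects who stayed on drug. The scores left out are those taken at stopping, where tolerability problems might show.

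The documents give some reason to look. Protocol 1.5.3 reports somnolence among the most common adverse events at 5 mg in the Phase 2 chronic pruritus trial (4.7%), and depression among the serious adverse events in the serlopitant group of the Phase 2 PN trial. HADS and ESS can pick up worsening that nobody reports as an adverse event. No efficacy conclusion or decision rule depends on these tables.

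**Working it through.** **The SAP's own example.** Appendix A counts Baseline as Day 1. Protocol 6.5.6 to 6.5.9 place Weeks 2, 4, 6 and 10 at 14, 28, 42 and 70 days after Baseline, that is on Days 15, 29, 43 and 71. The midpoints are:

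- Baseline and Week 2: (1 + 15)/2 = 8
- Weeks 2 and 4: (15 + 29)/2 = 22
- Weeks 4 and 6: (29 + 43)/2 = 36
- Weeks 6 and 10: (43 + 71)/2 = 57

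The values 22 and 36 match SAP 6.1.3 exactly, so its grid includes Weeks 2 and 6.

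**Mapping onto the shells.** There are 69 possible stop days (2 to 70). With the Week 4 visit on Day 29:

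| Stop day | Maps to | HADS/ESS table | Days |
|---|---|---|---|
| 2–21 | Week 2 or earlier | no on-treatment row | 20 |
| 22–29 | Week 4 | stopping score tabulated | 8 |
| 30–35 | Week 4 | Week 4 value kept, stopping score unused | 6 |
| 36–56 | Week 6 | Week 4 value kept, no row for stopping score | 21 |
| 57–70 | Week 10 | stopping score tabulated | 14 |

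The Week 4 visit window is Days 26 to 32. A subject who stops by Day 21 therefore normally has no Week 4 value to fall back on. The 6 days in the third row become 9 if the visit is on Day 26 and 3 if it is on Day 32.

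Shares of days: 20/69 = 29% with no on-treatment row; (6 + 21)/69 = 27/69 = 39% with only the stopping score lost; 22/69 = 32% tabulated.

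**Alternative grid.** If only the HADS/ESS visits (Days 1, 29, 71) were used, the midpoints would be 15 and 50. Days 2 to 14 (13/69 = 19%) would still have no row, and Week 4 would run to Day 49, which contradicts the SAP's Day 36 limit.

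**Subjects, by assumption only.** The documents give no discontinuation rate for this trial. Suppose 5%, 10% or 20% of 140 per arm stop early (7, 14 or 28 subjects), evenly over the 69 days, and all attend the discontinuation visit:

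- No on-treatment row: × 20/69 = 2.0, 4.1 or 8.1 per arm
- Only the stopping score lost: × 27/69 = 2.7, 5.5 or 11.0 per arm

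The nearest figure in the documents is the Phase 2 PN trial, with 128 subjects randomized 1:1. Stops for treatment-emergent adverse events alone, over 8 weeks, were 3/64 = 4.7% on serlopitant and 6/64 = 9.4% on placebo, taking 64 per arm.

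**The case against.** The case for leaving the plan alone has real weight.

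- **The tables do show size of worsening.** A reader might infer that nothing by arm shows how much anyone worsened. The shells do not support that: absolute change is given with its minimum and maximum, so the worst single change at each tabulated visit is visible. What is absent is a count of worsened subjects. With no cut-off for either scale in the documents, that absence is largely a matter of preference.
- **Other cover exists.** Somnolence, anxiety or depression reported as an adverse event is tabulated by arm, including events leading to discontinuation (Table 14.3.1.1.3). Reasons for stopping are in Table 14.0.1. Dated scores are in Listings 16.2.7.2.1 and 16.2.7.2.2. This cover is partial: listings do not summarise, and the ESS listing shell shows no total score.
- **The mapping rule has some room.** SAP 6.1.3 does not address instruments that skip a visit, and does not say their scores are discarded. But the full grid is the only one tested above that reproduces its example, and leaving the choice to programming is itself a reason to settle it.
- **Some stopping scores are weak evidence.** HADS asks about the prior week, so for stops on Days 2 to 7 (6 of the 20 days) it partly reflects time before treatment. The protocol does not fix the discontinuation visit relative to the last dose, so calling the score on-treatment is an assumption. Subjects lost to follow-up may have no score under any rule. All of this stands.
- **The signal is thin.** A reader might infer that the rule hides harm from serlopitant. The documents do not show this: in the Phase 2 PN trial more placebo than serlopitant subjects stopped for adverse events.

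**Conclusion.** The point holds as a limited gap. On the SAP's stated rule, HADS and ESS scores from stops on Days 2 to 21 and 36 to 56 reach no row in the by-arm tables, and a score mapped to Week 4 is unused when a Week 4 value exists. Subjects who stop before Day 22 normally appear only at baseline and, if they attend, at off-drug follow-up. This rests on the full-grid reading of SAP 6.1.3, which its own example supports.

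The size in patients is unknown. A reader might take 29% as the share of subjects lost; it is a share of calendar days. The illustrative 2 to 8 per arm depends on the assumed stopping rates, even spread and attendance. Nor are the data lost to the trial, since they remain in the listings. This is a cheap improvement to consider.

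**What to change.** Before unblinding, add to SAP 6.9.4.5 and 6.9.4.6, for HADS-Anxiety, HADS-Depression and ESS total, one descriptive by-arm summary of each subject's largest worsening from baseline. Use Week 4, Week 10 and every early-discontinuation score, whether or not it maps to a tabulated visit. A cumulative distribution avoids having to choose a cut-off. State how many subjects contribute, and the timing of the discontinuation score relative to last dose.

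Show follow-up separately. With a half-life of 45 to 86 hours (Protocol 1.5.1), 21 days (504 h) is 5.9 to 11.2 half-lives and 35 days (840 h) is 9.8 to 18.7, so those scores are effectively off drug. Keep the existing tables.

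The cost is SAP wording and three tables or figures from data already collected. There are two downsides:

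- The results will be noisy. With assumed worsening rates of 5% and 10% at 140 per arm, the standard error is √(0.05 × 0.95/140 + 0.10 × 0.90/140) = 0.0313, and the 95% interval for the difference is 5 ± 6.1 points, or −1.1 to 11.1.
- Subjects with more assessments have more chances to show worsening. The planned schedule limits this to two scores per subject (Week 4, plus Week 10 or the stopping score), and to one for those who stop before Week 4.
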